6.4.3 Additional study drug

Metformin, see above, see Section [6.4.2](#).

6.4.4 Labelling

The bulk supply of AZD 1656 will be labelled at Investigational Products, AstraZeneca R&D, Wilmington according to Good Manufacturing Practice (GMP). The IP will be labelled with a

2-panel label. One part of the label will be permanently affixed to the vial and the other part will be a peel-off part for insertion into the Drug Accountability document.

6.4.5 Storage

All study drugs must be kept in a secure place under appropriate storage conditions. The IP label on the bottle and the Investigator Brochure (IB) specifies the appropriate storage and shipment.

6.5 Concomitant and post-study treatment(s)

No oral anti-diabetic treatment apart from a stable dose of Metformin and study drug is allowed from 8 weeks before enrolment until the follow up visit.

No changes (initiation, dose change or cessation) in any current medication (including over the counter [OTC] products) are allowed from 4 weeks prior to randomisation until the follow up visit (except for drugs prescribed for occasional use, eg, paracetamol and nasal spray for nasal congestion).

Insulin, glitazones, warfarin and amiodarone are not allowed from 3 months before enrolment until the follow up visit.

Potent CYP450 inhibitors, eg, ketoconazole and macrolide antibiotics are not allowed from 14 days before randomisation until the follow up visit.

Anabolic steroids and systemic treatment with glucosteroids are not allowed from 3 month before enrolment (inhaled and local treatment allowed) until the follow up visit.

Other medication, which is considered necessary for the subject's safety and well-being, may be given at the discretion of the investigator.

If changes in current medication are necessary, the investigator must decide if the subject should remain in study or be dismissed from study. The subjects must be instructed that no new additional medication will be allowed without the prior consent of the investigator.

6.6 Treatment compliance

The administration of all medication (including IP) must be recorded in the appropriate sections of the CRF.

Compliance will be assured by supervised administration of the IP by the investigator or his/her delegate.

6.6.1 Accountability

The study drug provided for this study will be used only as directed in the study protocol.

The study personnel will account for all drugs dispensed and returned.

The study personnel will account for all unused drugs and for appropriate destruction. Certificates of delivery, destruction and return must be signed.

7. COLLECTION OF STUDY VARIABLES

7.1 Recording of data

The investigator will ensure that all data collected in the study are provided to AZ. He/she ensures the accuracy, completeness, legibility and timeliness of the data recorded in the appropriate sections of the paper CRF (pCRF) or electronic CRF (eCRF) and according to any instructions provided.

The PI will provide AZ with all data produced during the study from the scheduled study assessments. He/she ensures the accuracy, completeness, legibility, and timeliness of the data reported to AZ in the pCRF and in all required reports.

7.2 Screening and demography procedures

Each subject will undergo an enrolment (screening) medical examination within 28 days prior to Visit 3. This will consist of:

- Recording of demographic data - date of birth, sex, height, weight, race
- A standard medical/surgical history and a physical examination including general appearance, skin, lymph nodes, thyroid, musculoskeletal/extremities, cardiovascular system, respiratory system, abdomen and a neurological examination (reflexes only)
- T2DM history (year of diagnosis, any diabetic complications, current diabetes treatment)
- An ophthalmological examination if not done within 3 months
- A blood sample for standard clinical chemistry and haematology assessments, HbA1c, C-peptide and GAD antibodies and a mid-stream urine sample for urinalysis, and drugs of abuse screen
- A resting blood pressure and pulse measurement
- Recording of a resting 12-lead ECG
- A blood sample for test of hepatitis B surface antigen, antibodies to HIV and antibodies to hepatitis C virus.
- Female subjects: Blood sample for analyses of follicle-stimulating hormone (FSH)
- Habits of nicotine and alcohol use

7.2.1 Follow-up procedures

A similar post-study examination (excluding the demographic data, height, drug test, medical and surgical history) will be performed within 7 to 10 days after last dosing of IP.

7.3 Safety

It is of the utmost importance that all staff involved in the study is familiar with the content of this section. The PI is responsible for ensuring this.

7.3.1 Definition of adverse events

An AE is the development of an undesirable medical condition or the deterioration of a pre-existing medical condition following or during exposure to a pharmaceutical product, whether or not considered causally related to the product. An undesirable medical condition can be symptoms (eg, nausea, chest pain), signs (eg, tachycardia, enlarged liver) or the abnormal results of an investigation (eg, laboratory findings, electrocardiogram). In clinical studies, an AE can include an undesirable medical condition occurring at any time, including run-in or washout periods, even if no study treatment has been administered.

The term AE is used to include both serious and non-serious AEs.

7.3.2 Definitions of serious adverse event

A SAE is an AE occurring during any study phase (ie, run-in, treatment, washout, follow-up), that fulfils one or more of the following criteria:

- Results in death
- Is immediately life-threatening
- Requires in-patient hospitalisation or prolongation of existing hospitalisation
- Results in persistent or significant disability or incapacity
- Is a congenital abnormality or birth defect
- Is an important medical event that may jeopardise the subject or may require medical intervention to prevent one of the outcomes listed above

For further guidance on the definition of a SAE, see [Appendix B](#) to the CSP.

7.3.3 Recording of adverse events

AEs will be collected from the first administration of IP throughout the treatment period and including the follow-up period. AEs will be recorded during the study days at the investigational site and at the follow-up visit. Serious AEs will be recorded from the time when informed consent is obtained at the pre-entry visit until the follow-up visit.

Variables

The following variables will be recorded in the CRF for each AE: verbatim, date (time only during residential period) when the AE started and stopped, maximum intensity, whether the AE is serious or not, causality rating (Yes/No), action taken with regard to IP and outcome.

In addition, the following variables will be collected for all SAEs: Date AE met criteria for serious AE, Date Investigator aware of serious AE, AE is serious due to, Date of hospitalisation, Date of discharge, Probable cause of death, Date of death, Autopsy performed, Causality assessment in relation to Study procedure(s), Description of AE, Causality assessment in relation to Additional drug, Causality assessment in relation to Other medication.

The maximum intensity of each AE should be recorded and rated according to the following definitions:

- mild (awareness of sign or symptom, but easily tolerated)
- moderate (discomfort sufficient to cause interference with normal activities)
- severe (incapacitating, with inability to perform normal activities)

It is important to distinguish between serious and severe AEs. Severity is a measure of intensity whereas seriousness is defined by the criteria in Section 7.3.2. An AE of severe intensity need not necessarily be considered serious. For example, nausea that persists for several hours may be considered severe nausea, but not a SAE. On the other hand, a stroke that results in only a limited degree of disability may be considered a mild stroke but would be a SAE.

The Investigator will assess causal relationship between IP and AEs, and answer “yes” or “no” to the question “Do you consider that there is a reasonable possibility that the event may have been caused by the investigational product.

Causal relationship in cases where the disease under study has deteriorated due to lack of effect will be classified as no reasonable possibility.

For SAEs causal relationship will also be assessed for other medication and study procedure. Note that for SAEs that could be associated with any study procedure the causal relationship is implied as “yes”.

A guide to the interpretation of the causality question is found in [Appendix B](#) to the CSP.

Adverse Events based on signs and symptoms

All AEs spontaneously reported by the subject or reported in response to the open question from the study personnel: “*Have you had any health problems since the previous visit?*”, or revealed by observation will be collected and recorded in the

CRF. When collecting AEs, the recording of diagnoses is preferred (when possible) to recording a list of signs and symptoms. However, if a diagnosis is known and there are other signs or symptoms that are not generally part of the diagnosis, the diagnosis and each sign or symptom will be recorded separately.

Adverse Events based on examinations and tests

Deterioration as compared to baseline in protocol-mandated laboratory values, vital signs and other safety variables will only be reported as AEs if they fulfil any of the SAE criteria or are the reason for discontinuation of treatment with the IP. If a deterioration in a laboratory value/vital sign is associated with clinical signs and symptoms, the sign/symptom will be reported as an AE and the associated laboratory result/vital sign will be considered as additional information. Any new or aggravated clinically relevant abnormal medical finding at a physical examination as compared with the baseline assessment will be reported as an AE.

Clinically relevant deterioration in non-protocol-mandated measurements will be reported as AE(s).

Wherever possible the reporting investigator uses the clinical, rather than the laboratory term (eg, anaemia versus low haemoglobin value).

Follow-up of unresolved adverse events

Any AEs that are unresolved at the patient's last AE assessment in the study are followed up by the investigator for as long as medically indicated, but without further recording in the CRF. AZ retains the right to request additional information for any patient with ongoing AE(s)/SAE(s) at the end of the study, if judged necessary.

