AZD1656 will be administered twice daily (40 mg or 80 mg depending on tolerance), along with food, as an oral suspension on all days except Day 5 and 8, when the total daily dose (80 mg or 160 mg) will be administered as a single dose in the morning after an overnight fast. The AZD1656 formulation is oral suspension 25 mg/mL.

All subjects will keep their regular Metformin treatment (once daily [od] or bid), but switch to tablets provided by the site from Visit 2 through Visit 3.

On Day 5 and 8 subjects will or will not receive an intra muscular injection of 1 mg glucagon at 3 h post dose in a crossover manner.

Duration of treatment

Each subject will receive AZD1656 treatment for 8 days.

Outcome variable(s):

- Safety
Adverse events, blood pressure, pulse, plasma glucose, safety laboratory variables and ECG
- Pharmacokinetics (PK)
AUC₀₋₂₄, C_{max} and t_{max} will be calculated for AZD1656 and its metabolite, AZ12555623

- **Pharmacodynamics (PD)**

Plasma glucose level 20 minutes post release of the hypoglycaemic clamp, time to recovery from hypoglycaemia as well as plasma concentration values of glucose, insulin, C-peptide and the counter regulatory hormones norepinephrine, epinephrine, glucagon, cortisol and growth hormone

Statistical methods

The study data concerning safety variables, demographic variables and pharmacokinetic variables will be evaluated using descriptive statistics.

For the PD efficacy variables (glucose after 20 min and time to reach 3.5 and 5 mmol/L) confidence intervals (95%) will be presented. A mixed model ANOVA with fixed effects for sequence, period and treatment and a random effect for subject within sequence will be used..

All PD-variables will be presented with individual values and descriptive statistics by treatment (with and without glucagon).

| TABLE OF CONTENTS | PAGE |
|---|-------------|
| TITLE PAGE | 1 |
| PROTOCOL SYNOPSIS..... | 2 |
| TABLE OF CONTENTS..... | 6 |
| LIST OF ABBREVIATIONS AND DEFINITION OF TERMS | 10 |
| 1. IMPORTANT MEDICAL PROCEDURES TO BE FOLLOWED BY THE INVESTIGATOR | 12 |
| 1.1 Medical emergencies and AstraZeneca contacts | 12 |
| 1.2 Overdose | 13 |
| 1.3 Pregnancy..... | 13 |
| 2. INTRODUCTION | 14 |
| 2.1 Background | 14 |
| 2.2 Research hypothesis..... | 15 |
| 2.3 Rationale for conducting this study | 15 |
| 2.4 Benefit/risk and ethical assessment..... | 15 |
| 3. STUDY OBJECTIVES..... | 16 |
| 3.1 Primary objective | 16 |
| 3.2 Secondary objectives | 16 |

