2.4 Benefit/risk and ethical assessment

The subjects will be hospitalised during the study in order to carefully monitor glucose levels, achieve maximal tolerated dose of AZD1656 given twice-daily (bid) and avoiding spontaneous hypoglycaemia.

The dose will be titrated over two days up to the maximal tolerated dose, where it will be maintained for another two days. Giving the maximally tolerated bid dose of AZD1656 as a single dose after an overnight fast will induce hypoglycaemia in both treatment arms (Day 5 and Day 8). Insulin may be needed as a supplement in order to achieve stable glucose levels during these study days.

A glycaemic clamp with a continuously titrated glucose and/or insulin infusion (via an automated glucose clamp device, Biostator[®]) will be used to allow a controlled step-wise lowering of plasma glucose, and the plasma glucose level will not be allowed to be lower than 2.7 mmol/L

The recovery of plasma glucose will be measured with and without intramuscular glucagon. The Biostator[®] will also be used to guarantee a safe recovery of the plasma glucose levels.

In the ongoing SAD study (D1020C00001), single doses up to 180 mg AZD1656 have been given to healthy volunteers during euglycemic clamp and in the ongoing MAD study (D1020C00002) multiple oral doses of up to 80 mg AZD1656 have been given bid to patients with T2DM. These ongoing studies have not raised any safety concern.

All of the significant adverse findings seen in the toxicology studies are considered to be secondary to hypoglycaemia and/or relatively minor, reversible or can be monitored in clinical studies.

Careful monitoring regarding symptoms or laboratory abnormalities indicative of any adverse effects, including muscle symptoms, creatinekinase (CK) and aspartataminotransferas (AST) will be observed during the entire study.

Blood samples for deoxyribonucleic acid (DNA) extraction will be taken (optional) and DNA will be saved for potential future research into genes that may influence response to AZD1656.

There are no direct benefits for the subjects participating in this study.

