5.4.3 Study specific criteria for discontinuation

Events of hypoglycaemia (defined as plasma glucose <2.5 mmol/L (45 mg/dL), at 2 occasions or 1 event of hypoglycaemia that is difficult to cure despite glucose administration (according to the judgement of the investigator) or prolonged hyperglycaemia (defined as 2 consecutive days with fasting morning plasma glucose >15 mmol/L (270 mg/dL) should lead to discontinuation of treatment and the event should be reported as AE.

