7.3.5 Laboratory safety assessment

Blood and urine samples for determination of clinical chemistry, haematology and urinalysis parameters will be taken at the times given in the study plan. The date and time of collection will be recorded in the appropriate CRF section.

The following laboratory variables will be measured:

Laboratory variables:

Clinical chemistry

S-Albumin

S-ALT

S-AST

S-Alkaline phosphatase

S-Bilirubin, total

S -Calcium, total

S -Creatinine

S –CRP

S- γ -GT

Haematology

B-Haemoglobin

B-Leukocyte count

B-platelet count

B-Leukocyte differential count (absolute count)

Urinalysis

U-Hb

U-Protein

U-Glucose

S-Potassium

S-Sodium

S-Creatine kinase

P-Glucose

P-Prothrombin complex (INR)^a

^a Only on Visit 1 and pre dose Day 9.

The blood samples for the clinical chemistry and haematology will be analysed using routine methods at the contracted Laboratory, Covance. Urine samples will be analysed at the CRO by urine dipsticks. Laboratory values outside the reference limits suspected to be of any clinical significance will be re-checked. Subjects in whom the suspected clinical significance is confirmed at the repeated sampling will either not be included or, if already included, will be followed until normalisation or for as long as the investigator considers necessary.

At screening visit, all subjects will be tested for HIV, hepatitis B and C. Samples for C-peptide and GAD antibodies will also be taken as well as FSH for women unless age >50 years and 2 years without menstruation periods.

Urine will be tested for the following drugs of abuse: amphetamine, barbiturates, benzodiazepines, cannabinoid, cocaine, opiates and methadone.

If a subject tests positive for drugs of abuse they will be excluded from entering, or continuing in, the study.

For blood volume see Section 8.1.

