12. EVALUATION AND CALCULATION OF VARIABLES BY CRO

12.1 Calculation or derivation of safety variable(s)

12.1.1 Other significant adverse events (OAE)

During the evaluation of the AE data, an AZ medically qualified expert will review the list of AEs that were not reported as SAEs and discontinuation due to adverse events (DAEs). Based

on the expert's judgement, significant adverse events of particular clinical importance may, after consultation with the Global Drug Safety Physician, be considered OAEs and reported as such in the CSR.

Examples of these are marked haematological and other laboratory abnormalities, and certain events that lead to intervention (other than those already classified as serious), dose reduction or significant additional treatment.

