13.2.4 Safety

AEs will be presented as number of patients with at least one AE, and will be further detailed by presenting the categories fatal AEs, serious non-fatal AEs and AEs leading to treatment discontinuation. All AEs should be summarized by the preferred term, assigned to the event using MedDRA vocabulary, for the periods on treatment, during follow-up and during study. Treatment period is defined as from date for start of study drug to date of last study drug or, when time is available, from time for start of study drug to 24:00 the date of last study drug or until the start of the next study drug if there are multiple exposures without a washout period. A follow-up period should capture any event occurring after the last treatment period up to the end of study for the patient, eg, the patient's last visit in the study. AEs will be represented in each period where there is overlapping occurrence.

Actual values and change from baseline for laboratory variables will be presented descriptively by treatment and time. Shift-tables will be used to classify the subjects in the categories below, within and above upper limit of normal (ULN), pre-treatment versus post-treatment. Pre-entry versus follow-up for laboratory variables will be presented in shift plots. A list with abnormal (out of reference range) laboratory values will be presented. For each abnormal value all values for that specific laboratory variable will be presented for the subject with the abnormal value. If a subject has more than one observation on the same measurement occasion, the results from the earliest draw should be used in all summaries.

Actual values and change from baseline for vital signs (BP, pulse and weight) will be presented descriptively by treatment and time.

All abnormal physical examination findings and ECG assessments will be listed. Any new or aggravated abnormal findings as compared to the baseline assessment will be listed.

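### A first, symptom-free plasma glucose below 2.5 mmol/L that is treated with rescue glucose is not recorded as an adverse event, so it never reaches the review for other significant adverse events (minor)

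*Protocol*

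**What the plan says.** Section 7.3.3, under AEs based on examinations and tests, covers worsening from baseline on tests that the protocol schedules, whether laboratory, vital signs or another safety measurement. Such changes "will only be reported as AEs if they fulfil any of the SAE criteria or are the reason for discontinuation of treatment with the IP". When symptoms accompany the change, the symptom is the AE and the value is supporting information. Clinically relevant changes in measurements that the protocol does not mandate are AEs. Causality, action taken with IP and outcome are recorded for each AE.

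The synopsis gives the safety variables as "Adverse events, blood pressure, pulse, plasma glucose, safety laboratory variables and ECG".

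Section 4.1.2 gives about 25 g oral glucose for a plasma glucose below 2.5 mmol/L in the residential period, except 0-6 h post dose on Days 5 and 8. Rescue during titration also means a lower AZD1656 dose. Rescue after the initial dose means discontinuation. Under 5.4.3, two values below 2.5 mmol/L, or one that proves hard to correct, "should lead to discontinuation of treatment and the event should be reported as AE".

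Under 12.1.1 a medical expert "will review the list of AEs that were not reported as SAEs and discontinuation due to adverse events (DAEs" and may class some of them as other significant adverse events (OAEs). On what qualifies, the section says: "Examples of these are marked haematological and other laboratory abnormalities, and certain events that lead to intervention"; it goes on to name dose reduction and added treatment. The abbreviation list defines an OAE as a kind of AE.

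For laboratory data, 13.2.4 gives summaries, shift tables and this output: "A list with abnormal (out of reference range) laboratory values will be presented".

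**The concern.** For an isolated abnormality on a scheduled test, the two conditions that make it an AE (serious, or the reason for stopping IP) are the same two that take it off the list reviewed for OAEs. The OAE category exists for important events that are neither, and 12.1.1 illustrates it with laboratory abnormalities, interventions and dose reductions.

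Glucose is where this bites. AZD1656 lowers glucose, the protocol titrates it to the highest tolerated dose, and safety and tolerability is a secondary objective. A low value that needed treatment and a dose cut is the sort of event a reader would expect to find among the AEs, with the investigator's view on cause. Under the present wording a site that follows 7.3.3 literally would not record it. A site that enters hypoglycaemia as a diagnosis would, citing the general AE definition in 7.3.1, which includes abnormal test results.

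**Working it through.** No arithmetic is needed for the conclusion. The check is to follow each kind of event through the rules.

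**Plasma glucose below 2.5 mmol/L at a scheduled measurement, outside 0-6 h post dose on Days 5 and 8**

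| Case | Rule | AE? | On the list reviewed under 12.1.1? |
|---|---|---|---|
| Meets an SAE criterion | 7.3.2, 7.3.3 | Yes | No, removed as SAE |
| Second occasion, or hard to correct | 5.4.3 | Yes | No, removed as DAE |
| Rescue after the initial dose | 4.1.2 (discontinue), 7.3.3 | Yes | No, removed as DAE |
| With symptoms, not serious, IP continued | 7.3.3 | Yes, the symptom | Yes |
| First, no symptoms, easily corrected, later than the initial dose, IP continued | 4.1.2, 7.3.3 | No | No |

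The last row is the gap. Example: on Day 2, at 80 mg bid, one of the seven bedside values is below 2.5 mmol/L without symptoms. The subject gets about 25 g glucose and the dose goes back to 40 mg bid. The event led to an intervention and a dose reduction, both named in 12.1.1, yet it is not an AE. The restriction comes from the word only in 7.3.3. Section 5.4.3 does not itself say that other low values are not AEs; it requires an AE for events that lead to discontinuation and is silent on the rest.

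**Occasions.** Table 3 schedules 7 bedside values on each of Days 1, 2, 3, 4, 6 and 7: 7 × 6 = 42 per subject, of which the Day 1 pre-dose value precedes the first dose. This counts opportunities and says nothing about how often a value falls below 2.5 mmol/L.

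**Laboratory values.** A marked CK or AST rise at a scheduled draw, with no symptoms, not serious and IP continued, follows the same path: not an AE, so not on the 12.1.1 list. Section 2.4 singles these tests out: "laboratory abnormalities indicative of any adverse effects, including muscle symptoms, creatinekinase (CK) and aspartataminotransferas (AST) will be observed". Section 7.3.5 has values suspected to be clinically significant re-checked and says that confirmed cases, "if already included, will be followed until normalisation or for as long as the investigator considers necessary", without saying that they become AEs. Whether a re-check counts as protocol-mandated is not stated.

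**What is still captured.** Laboratory values go to the 13.2.4 summaries and abnormal-value list. That includes the laboratory P-Glucose in 7.3.5, drawn in Visit 3 on Days 1, 5, 6, 8 and 9. Bedside glucose, the only glucose measured on Days 2, 3, 4 and 7, is not clearly covered by a list of laboratory values. Section 6.6 records administration of all medication, so a dose cut can be seen in the CRF. Causality and outcome for the event are not collected.

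**The case against.** The strongest reply is that nothing here is contradictory. OAEs are defined as a subset of AEs, so it is the definition at work when something that is not an AE cannot be an OAE. Limiting AEs from scheduled tests to serious, discontinuing or symptomatic changes is a legitimate choice. That stands as far as it goes.

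A reader might also infer that the laboratory examples in 12.1.1 describe an empty class. The documents do not support that. A laboratory abnormality with symptoms puts the symptom on the AE list with the value attached, and clinically relevant results from non-mandated measurements are AEs. Follow-up sampling under 7.3.5 may come in that way.

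Nor do the documents support the inference that abnormal laboratory findings are lost. Section 13.2.4 lists them with all of that subject's values for the variable, and with 10 subjects each can be read individually.

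Finally, the glucose case is narrow: most low values would be symptomatic, repeated, hard to correct or serious, and so be AEs already. That limits the frequency but does not close the gap. The remaining event was treated, may have changed the dose, and has no assured place in the planned safety output.

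**Conclusion.** The point holds, at minor severity, for a first, symptom-free, easily corrected scheduled plasma glucose below 2.5 mmol/L that is given rescue glucose. Such an event gets no AE record, no causality rating and no outcome, and cannot reach the OAE review, although 12.1.1 gives intervention and dose reduction as examples. For isolated, symptom-free, non-serious laboratory abnormalities with IP continued the route is closed too, but the values are listed and tabulated, so that part is a lesser point.

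The size cannot be given as a number: the documents state no event rate, and the titration thresholds in Figure 2 are not shown. The conclusion rests on reading the specific rule in 7.3.3 as overriding the general AE definition in 7.3.1, and on bedside glucose being a protocol-mandated safety variable, which the synopsis and Table 3 support. The primary variable and its analysis are untouched.

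**What to change.** **Main change, 7.3.3.** Add a sentence: a scheduled plasma glucose below 2.5 mmol/L that is given rescue treatment, outside 0-6 h post dose on Days 5 and 8, is reported as an AE with causality, action taken with IP and outcome. The deliberate clamp hypoglycaemia stays excluded, and titration decisions made without rescue do not become AEs.

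**Secondary change, 12.1.1.** Have the medical expert also consult the abnormal laboratory list from 13.2.4, and have any value judged to be of particular clinical importance recorded as an AE before it is classed as an OAE. Recording it first keeps the OAE definition in the abbreviation list true and obtains the causality rating and outcome; letting the expert label a bare value would do neither. Section 7.3.3 needs a short cross-reference allowing this exception, and the review should take place before clean file so that the investigator can still complete the AE form.

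**Cost.** About one sentence in each section, plus the cross-reference; the AE form and the list already exist. The downside is a few extra AEs that partly duplicate reported values, and brief extra expert review. The rescue, titration and discontinuation rules and the primary analysis do not change.
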